samples (may be drawn after randomization but must be drawn prior to treatment), endocervical specimen to be sent to Yale Pathology for high-risk HPV DNA testing (if high-risk HPV DNA results are already available, this testing may not have to be repeated) and a second endocervical cytobrush specimen for translational research purposes. Blood samples will be collected in sodium heparin tubes with about 28 cc collected each time as follows: 7 cc in each of 3 green top tubes and 7 cc in 1 EDTA/purple top tube (see follow up visits below). Endocervical specimen for high-risk HPV DNA test to be performed by Yale Pathology will be submitted in usual fashion as a SurePath specimen. Endocervical cytobrush sample for study purposes will be collected into a 50ml conical tubes containing PBS using sterile techniques and will be stored on ice until picked up by a laboratory personnel. Once all eligibility has been met the subject will be randomized to one of three arms.

Additional components of visit outline by study group:

- (1) Control group: Observation at specified study timepoints.
- (2) Imiquimod only: At the baseline visit, this group will receive instruction on imiquimod self application (16 week course) using a 6.25 mg vaginal suppository, storage of medication, possible side effects. Subjects will be provided a diary and case report form to record vaginal suppository application and side effects will be recorded per NCI Common Terminology Criteria for Adverse Events (CTCAE 4.0). Imiquimod self-application regimen will be similar to one previously described²⁴ and is as follows:
- Treatment weeks 1 and 2: Subjects apply one vaginal suppository per week
- Treatment weeks 3 and 4: Subjects apply two vaginal suppositories per week
- Treatment weeks 5 to 16: Subjects apply three vaginal suppositories per week

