10.0 EVALUATION CRITERIA

10.1 Objective Response

The major parameters of response to be assessed include treatment efficacy defined as histologic regression of cervical dysplasia to CIN 1 or less 12 to 16 weeks after the end of imiquimod treatment, HPV clearance and treatment tolerance.

- 10.11 Histologic regression: Only subjects with histologically confirmed CIN 2,3 as reviewed by a central study pathologist will be enrolled in the study. All index biopsy sites noted to have CIN 2,3 at baseline must be assessed via colposcopy. Cervical biopsy at the final colposcopy will be collected from the worst areas of residual disease. Included in the evaluations are the following criteria:
 - Histologic regression (HR): Histologic regression of all index lesions to CIN 1 or less at 12 to 16 weeks after end of imiquimod treatment period.
 - Histologic remission (HM): Complete regression of cervical dysplasia at all index biopsy sites at 12 to 16 weeks after end of imiquimod treatment period.
 - Persistent Disease (PR): One or more index lesions persists with CIN 2,3 high grade dysplasia or new lesions are identified colposcopically and histologically confirmed to be CIN 2,3.
 - Progressive Disease (PD): Worsening histology of an index lesion.
- 10.12 HPV Clearance: HPV clearance will be measured by both the Roche cobas HPV Test utilized by pathology concomitant with the pap test at final study visit which assesses for presence of 14 high risk HPV types as well as HPV 16/18 genotyping performed by [name] Lab.
- 10.13 Treatment Tolerance: The grade level of the various toxicities will be classified using the Common Toxicity Criteria, version 4 (CTC, v.4) guidelines. Acute toxicities will be scored if occurring </= 30 days from treatment completion, and chronic if > 30 days. Frequency and duration of treatment interruptions due to the treatment toxicity will be assessed.

11.0 **DURATION OF STUDY**

11.1 This study will continue as long as treatment protocols remain activated.

HIC#: 1603017415 Protocol version 11.0

CIN 2/3

11.2 The subject will be followed with routine clinical care with a 6 month colposcopy and cytology if histologic remission or regression noted at final study visit and in 12 months if cytology remains negative with normal colposcopy. Any abnormal cytology or colposcopy at 6 months should prompt cervical biopsy and management per guidelines of American Society for Colpsocpy and Cervical Pathology (ASCCP).

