12.9.4 Adverse Event Reporting Period

The study period during which all AEs and SAEs must be reported begins after informed consent

is obtained and initiation of study treatment and ends 30 days following the last administration of

study treatment or study discontinuation/termination, whichever is earlier. After this period,

investigators should only report SAEs that are attributed to prior study treatment.

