or SAE only if the frequency, severity, or character of the condition worsens during the study.

When reporting such events, it is important to convey the concept that the preexisting condition

has changed by including applicable descriptors (e.g., "more frequent headaches").

d. Hospitalizations for Medical or Surgical Procedures

Any AE that results in hospitalization or prolonged hospitalization should be documented and

reported as an SAE.

HIC#: 1603017415

Protocol version 11.0

Version date: December 20, 2022

APPROVED BY THE YALE UNIVERSITY IRB 2/24/2023

CIN 2/3

31

If a subject is hospitalized to undergo a medical or surgical procedure as a result of an AE, the

event responsible for the procedure, not the procedure itself, should be reported as the SAE. For

example, if a subject is hospitalized to undergo coronary bypass surgery, record the heart condition

that necessitated the bypass as the SAE.

Hospitalizations for the following reasons do not require reporting:

Hospitalization or prolonged hospitalization for diagnostic or elective surgical procedures for

preexisting conditions

Hospitalization or prolonged hospitalization required to allow efficacy measurement for the study

or

Hospitalization or prolonged hospitalization for scheduled therapy of the target disease of the

study.

e. Pregnancy

If a female subject becomes pregnant while receiving imiquimod or 9-valent HPV vaccine series

or within 30 days of awareness after the last dose of study drug, a report should be completed and

expeditiously submitted to Yale HIC. Follow-up to obtain the outcome of the pregnancy should

also occur.

Abortion of a pregnancy in a study subject receiving Imiquimod, whether accidental, therapeutic,

or spontaneous, should always be classified as serious, and expeditiously reported as an SAE.

Similarly, any congenital anomaly/birth defect in a child born to a female subject exposed to

imiquimod or 9-valent HPV vaccine should be reported as an SAE.

f. Post-Study Adverse Events

The investigator should expeditiously report any SAE occurring after a subject has completed or

discontinued study participation if attributed to prior Imiquimod or 9-valent HPV vaccine

exposure.

If the investigator should become aware of the development of cancer or a congenital anomaly in

a subsequently conceived offspring of a female subject who participated in the study, this should

be reported as an SAE.

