15.2 Analysis Set Definitions

- **full analysis set**—all randomized subjects
- safety analysis set—all subjects who have received at least one dose of any study drug, and/or have had any assessments at baseline or later that could be associated with an AE; analyzed by treatment received
- ITT analysis set—all randomized subjects with valid baseline measurements; analyzed by treatment assigned
- modified ITT analysis set—all randomized subjects with valid baseline measurements, receiving at least one dose of any study drug, and have at least one valid post-baseline measurement of outcome; analyzed by treatment assigned

HIC#: 1603017415 Protocol version 11.0

- modified ITT completers analysis set—all randomized subjects who receive at least one dose of
 any study drug and have complete and valid post-baseline assessments of outcome; analyzed by
 treatment assigned
- **per protocol analysis set**—all randomized subjects who receive all doses of their assigned study drug, have complete and valid post-baseline assessments of outcome, and have no protocol deviations (e.g. dose modification, assessment outside of time window, non-compliance)

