15.8 Sample Size Justification

Anticipated annual accrual is approximately 40-45 subjects.

Our general philosophy regarding Phase II trials of new drug combinations is to facilitate the prompt discovery of inactive agents, yet allow for a reasonable estimate of the response rates for those regimens demonstrating some degree of activity. However, excessive accrual to inactive study regimens to document precise response rates is to be avoided. The purpose of this study is to evaluate the activity and potential toxicity of the combination therapy of Imiquimod + HPV vaccine in subjects with untreated high-grade CIN 2,3 cervical dysplasia. This study will implement a 3 arm randomized trial design that will allow us to estimate the treatment effect of Imiquimod + HPV vaccine compared to observation as well as Imiquimod alone compared to observation.

Based on published literature for the primary outcome,³⁸ we assume a 28% spontaneous histological regression rate in CIN 2-3 lesions with observation alone (control group). From Grimm et al.'s efficacy

HIC#: 1603017415 Protocol version 11.0

trial of imiquimod for treatment of CIN 2-3, we would like to have sufficient power to detect a 35% absolute increase in rate of histologic regression in the imiquimod only arm compared to control. Based on this data, we consider a conservative effect size estimate also of an absolute 35% higher rate of histologic regression in the imiquimod + HPV vaccine intervention arm compared with the control arm. We therefore aim to recruit a total sample size of 114 subjects (38 in each arm). Calculations based on Fisher's Exact Test indicate we will have $\geq 90\%$ power to detect a treatment effect of $\geq 29\%$ in both treatment arms independently compared to the observation arm ($\alpha = 0.025$ for each comparison to control). In addition, with n = 38 subjects per arm, we would have 80% power to detect a treatment effect size of $\geq 25\%$ in one treatment arm compared to placebo (while maintaining 90% power to detect the treatment effect size of $\geq 25\%$ in the other arm). Assuming a subject dropout rate of 20%, a total sample size of 138 (n = 46 per arm) subjects is calculated which will be recruited over 5 years.

Some operating characteristics of the study design are as follows:

Exact Operating Characteristics for the Treatment Effect Size Δ given control group rate=0.28, n=38 subjects per arm, one-sided α

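### Section 12.9.4 gives the observation arm no start for adverse-event reporting and normally closes the period before the week-22 visit, in conflict with 9.1, 10.13, 15.2 and 15.4

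*Combined protocol and SAP*

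**What the plan says.** Section 12.9.4 sets the only stated AE reporting period. It opens after consent "is obtained and initiation of study treatment and ends 30 days following the last administration of" the study drug. The same sentence allows an earlier close: "study treatment or study discontinuation/termination, whichever is earlier". After it closes, "investigators should only report SAEs that are attributed to prior study treatment". Section 12.10.2(f) agrees on that last point: a late SAE, in a subject who has finished or "discontinued study participation if attributed to prior Imiquimod or 9-valent HPV vaccine", is still to be reported.

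Other sections imply a wider period:

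- **Arms (6.2.1):** "1) Control group: Observation at specified study timepoints". No study drug is given.
- **Schedule (9.1):** toxicity assessment before treatment and at weeks 8, 16 and 22, with no restriction by arm.
- **Tolerance (10.13):** "Acute toxicities will be scored if occurring </= 30 days from treatment completion, and chronic if > 30 days".
- **AE definition (12.9.1.1):** complications of mandated procedures, with cervical biopsy as the example, count as AEs. Section 6.2.2 has every subject biopsied at the final visit.
- **Safety set (15.2):** besides dosed subjects, it admits those who "have had any assessments at baseline or later that could be associated with an AE".
- **Safety tables (15.4):** AEs and SAEs are reported by treatment group on that set.

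**The concern.** The start and the main end point in 12.9.4 are both tied to dosing, and one of the three arms is never dosed. Read literally, the condition that opens reporting is not met for any control. In the treated arms the end falls before the visit at which all subjects are biopsied and toxicity is assessed for the last time. It also falls exactly where 10.13 starts to call toxicity chronic.

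At stake is the tolerability objective (1.2.3). If some staff follow 12.9.4 and others follow the 9.1 schedule, recorded AEs will differ by arm for reasons unrelated to treatment. The by-arm tables would then be hard to interpret, and analysis cannot recover events that were never recorded. Part of the AE definition makes this worse: two of the four examples in 12.9.1.1 (new events, and worsened pre-existing conditions) refer to the protocol's reporting period, which controls do not have.

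**Working it through.** This is calendar arithmetic. The one stated figure to reproduce is the timing of the final visit.

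**1. Schedule.** Section 1.1 puts the final assessment at weeks 20–24, 4 to 8 weeks after imiquimod ends: 16 + 4 = 20 and 16 + 8 = 24. The boxes dispensed also fit a week-16 end: 2×1 + 2×2 + 4×3 = 18 for weeks 1–8, and 8×3 = 24 for weeks 9–16. The last scheduled dose is therefore no later than day 16×7 = 112. The visit window is days 140–168, nominally day 154.

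**2. Closing date.** 112 + 30 = day 142, and 142/7 = week 20.3.

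- Gap to the nominal visit: 154 − 142 = 12 days. Gap to the latest visit: 168 − 142 = 26 days.
- Share of the visit window after closure: 26/28 = 93%. It is 100% if the last dose is on day 110 or earlier, since 110 + 30 = 140.

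**3. Extended dosing.** Section 6.2.1, under the combination arm, lets dosing be extended but gives no length. Extensions of 1 to 4 weeks are assumed here, with the visit at least 21 days after the last dose.

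| Extension | Closes | Permitted visit days | Share after closure |
|---|---|---|---|
| 0 weeks | 142 | 140–168 | 26/28 = 93% |
| 1 week | 149 | 140–168 | 19/28 = 68% |
| 2 weeks | 156 | 147–168 | 12/21 = 57% |
| 3 weeks | 163 | 154–168 | 5/14 = 36% |
| 4 weeks | 170 | 161–168 | 0% |

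**4. Events asked about at week 22.** These include events that began after the week-16 visit. On nominal timing that interval is 154 − 112 = 42 days, of which 142 − 112 = 30 are inside the period: 30/42 = 71%, if onset is uniform. With visits on days 126 and 168 it is 16/42 = 38%; with the final visit on day 140 it is 100%.

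**5. Chronic toxicity.** The cut-off in 10.13 (more than 30 days after treatment completion) and the close in 12.9.4 (30 days after the last administration) coincide. Non-serious toxicity that is chronic by onset is therefore never inside the period. Attributed SAEs are the stated exception.

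**6. Controls.** 46/138 = 1/3 as planned, and 38/114 = 1/3 before the dropout allowance (15.8: "a total sample size of 138 (n = 46 per arm) subjects is calculated"). The discontinuation/termination clause could close their period, but nothing opens it.

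**7. A related conflict.** Section 10.1 places response assessment 12 to 16 weeks after imiquimod, against 4 to 8 weeks in 1.1. On the 10.1 timing (weeks 28–32) the final assessment would lie wholly outside the period. The two sections must be reconciled.

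**The case against.** The strongest reply is that 12.9.4 governs what must be reported, not what is collected. Section 9.1 schedules toxicity assessment without restriction by arm, 12.10.1 asks for a consistent method of eliciting AEs at every evaluation, and 12.9.3 covers AEs observed throughout the study. A 30-day period after the last dose, with attributed SAEs reportable beyond it, is also a deliberate and defensible choice.

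Much of this stands, and it rules out several stronger inferences a reader might draw:

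- **No AE data on controls.** Their start is undefined, and that does not show that nothing is recorded.
- **Most week-22 events lost.** This is true of events starting at or after the visit on the 16-week schedule. It is not true of events since week 16 elicited there (71% of onset time is inside on nominal timing), and extended dosing narrows the gap.
- **All chronic toxicity missed.** Treatment-attributed SAEs remain reportable, and week 22 provides a visit at which to score the rest.
- **A biased safety comparison.** Section 15.6 plans descriptive statistics only, so no safety test is affected.
- **Early stoppers lose follow-up.** The reporting period can close early, but the documents do not cancel visits when imiquimod stops. For illustration, a last imiquimod dose at the end of week 6 gives (42 + 30)/7 = week 10.3. A week-8 booster in a previously unvaccinated combination-arm subject would move this to (56 + 30)/7 = week 12.3.

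The reply does not remove the conflict. The schedule and the safety set presuppose AE data from controls and from week 22, while the only section that defines a period excludes or omits them. Section 6.2.2 adds to the asymmetry: its side-effect case report forms are described only for the treated arms.

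**Conclusion.** The point holds as an inconsistency between sections with a real risk to ascertainment. One third of subjects have no defined start for AE reporting. On the 16-week schedule the period ends at about week 20.3, 12 days before the nominal final visit and before 93% of the days on which that visit may fall. Complications of the final biopsy then usually lie outside it, as does all non-serious toxicity with onset more than 30 days after treatment.

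This rests on a last dose on day 112 and a final visit in weeks 20–24; a longer dosing course shrinks the shortfall, to nothing at an assumed four weeks. The consequence is possible unequal ascertainment in descriptive by-arm safety tables. The efficacy analysis is untouched, and the documents do not show that control or late events go unrecorded.

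**What to change.** Rewrite 12.9.4 so that all three arms share:

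- one start, either consent or randomisation;
- one end, the final study visit or 30 days after the last dose if that is later;
- continued reporting of treatment-attributed SAEs afterwards, as 12.9.4 and 12.10.2(f) already require.

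Align 10.13 with this: state that chronic toxicity is scored up to the same end, and that the acute/chronic split applies to the treated arms, since controls have no treatment completion from which to count. An end at the final visit takes in events that begin there, but not a biopsy complication that begins later. If those are wanted, the section should say how they are captured.

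The cost is protocol wording and slightly more AE data entry. For a last dose on day 112, the change adds 12 days of reporting with a visit on day 154 and 26 days with a visit on day 168. No visit or procedure is added.

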12.9.5 Assessment of Adverse Events

All AEs and SAEs whether volunteered by the subject, discovered by study personnel during

questioning, or detected through physical examination, laboratory test, or other means will be

reported appropriately.

Each reported AE or SAE will be described by its duration (i.e., start and end dates), regulatory

seriousness criteria if applicable, suspected relationship to imiquimod or 9-valent HPV vaccine

(see following guidance), and actions taken.

To ensure consistency of AE and SAE causality assessments, investigators should apply the

following general guideline:

Yes

HIC#: 1603017415 Protocol version 11.0

CIN 2/3 29

There is a plausible temporal relationship between the onset of the AE and administration of imiquimod or 9-valent HPV vaccine and the AE cannot be readily explained by the subject's clinical state, intercurrent illness, or concomitant therapies; and/or the AE follows a known pattern of response to imiquimod or 9-valent HPV vaccine and/or the AE abates or resolves upon discontinuation of imiquimod or dose reduction and, if applicable such as in case of 9-valent HPV vaccine, reappears upon re-challenge.

No

Evidence exists that the AE has an etiology other than imiquimod or 9-vvalent HPV vaccine (e.g., preexisting medical condition, underlying disease, intercurrent illness, or concomitant medication); and/or the AE has no plausible temporal relationship to imiquimod or 9-valent HPV vaccine administration (e.g., cancer diagnosed 2 days after first dose of study drug).

Expected adverse events are those adverse events that are **listed** or characterized in the Package Insert or current Investigator Brochure.

Unexpected adverse events are those **not listed** in the Package Insert (P.I.) or current Investigator Brochure (I.B.) or not identified. This includes adverse events for which the specificity or severity is not consistent with the description in the P.I. or I.B. For example, under this definition, hepatic necrosis would be unexpected if the P.I. or I.B. only referred to elevated hepatic enzymes or hepatitis. **Refer to Section 13.0 for further guidelines**.

12.10 PROCEDURES FOR ELICITING AND RECORDING ADVERSE EVENTS

12.10.1 Eliciting Adverse Events

A consistent methodology for eliciting AEs at all subject evaluation time points should be adopted. Examples of non-directive questions include:

"How have you felt since your last clinical visit?

"Have you had any new or changed health problems since you were last here?"

12.10.2 **Specific Instructions for Recording Adverse Events**

Investigators should use correct medical terminology/concepts when reporting AEs or SAEs. Avoid colloquialisms and abbreviations. All information will be recording using Oncore Clinical Trials Management System.

HIC#: 1603017415 Protocol version 11.0

CIN 2/3

30

a. Diagnosis vs. Signs and Symptoms

If known at the time of reporting, a diagnosis should be reported rather than individual signs and

symptoms (e.g., record only liver failure or hepatitis rather than jaundice, asterixis, and elevated

transaminases). However, if a constellation of signs and/or symptoms cannot be medically

characterized as a single diagnosis or syndrome at the time of reporting, it is ok to report the

information that is currently available. If a diagnosis is subsequently established, it should be

reported as follow-up information.

b. Deaths

All deaths that occur during the conduct of the research must be reported to the Yale Principal

Investigator and the Remote Monitoring Coordinator immediately (if possible) to ensure that all

over site committees are properly informed. All information will be entered into Oncore Clinical

Trials Management System and updated appropriately. Further determination regarding the need

to submit to the subjects local IRB, Yale University HHRP following IRB Policy 710 for reporting

Unanticipated Problems Involving Risk to Subjects will be reviewed. Specific information is

outlined in section 13.0 of the protocol.

When recording a death, the event or condition that caused or contributed to the fatal outcome

should be reported as the single medical concept. If the cause of death is unknown and cannot be

ascertained at the time of reporting, report "Unexplained Death".

c. Preexisting Medical Conditions

A preexisting medical condition is one that is present at the start of the study. Such conditions

should be reported as medical and surgical history.

A preexisting medical condition should be re-assessed throughout the trial and reported as an AE

or SAE only if the frequency, severity, or character of the condition worsens during the study.

When reporting such events, it is important to convey the concept that the preexisting condition

has changed by including applicable descriptors (e.g., "more frequent headaches").

d. Hospitalizations for Medical or Surgical Procedures

Any AE that results in hospitalization or prolonged hospitalization should be documented and

reported as an SAE.

HIC#: 1603017415

Protocol version 11.0

Version date: December 20, 2022

APPROVED BY THE YALE UNIVERSITY IRB 2/24/2023

CIN 2/3

31

If a subject is hospitalized to undergo a medical or surgical procedure as a result of an AE, the

event responsible for the procedure, not the procedure itself, should be reported as the SAE. For

example, if a subject is hospitalized to undergo coronary bypass surgery, record the heart condition

that necessitated the bypass as the SAE.

Hospitalizations for the following reasons do not require reporting:

Hospitalization or prolonged hospitalization for diagnostic or elective surgical procedures for

preexisting conditions

Hospitalization or prolonged hospitalization required to allow efficacy measurement for the study

or

Hospitalization or prolonged hospitalization for scheduled therapy of the target disease of the

study.

e. Pregnancy

If a female subject becomes pregnant while receiving imiquimod or 9-valent HPV vaccine series

or within 30 days of awareness after the last dose of study drug, a report should be completed and

expeditiously submitted to Yale HIC. Follow-up to obtain the outcome of the pregnancy should

also occur.

Abortion of a pregnancy in a study subject receiving Imiquimod, whether accidental, therapeutic,

or spontaneous, should always be classified as serious, and expeditiously reported as an SAE.

Similarly, any congenital anomaly/birth defect in a child born to a female subject exposed to

imiquimod or 9-valent HPV vaccine should be reported as an SAE.

f. Post-Study Adverse Events

The investigator should expeditiously report any SAE occurring after a subject has completed or

discontinued study participation if attributed to prior Imiquimod or 9-valent HPV vaccine

exposure.

If the investigator should become aware of the development of cancer or a congenital anomaly in

a subsequently conceived offspring of a female subject who participated in the study, this should

be reported as an SAE.

